8.2.7 Patient reported outcomes (PRO)

–PRO” is an umbrella term referring to all outcomes and symptoms that are directly reported by the patient. PROs have become a significant endpoint when evaluating effectiveness of treatments in clinical studies. The following PROs will be administered in this study: EORTC QLQ-C30 v3 (core questionnaire), EORTC QLQ-LC13 (lung cancer module), patient-reported outcomes version of the CTCAE (PRO-CTCAE). (see [Appendix H and I](#)).

The PRO instruments will be completed by the patients using a paper format questionnaire on day 1 of every cycle. All assessments should be completed without assistance from anyone according to the assessment schedules. It takes approximately 30 minutes for patients to complete the questionnaires; therefore, the burden to the patient is moderate.

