For each of the symptoms scales/items in the EORTC QLQ-C30 questionnaire, time to symptom deterioration will be defined as the time from start of study drug until the date of the first clinically meaningful symptom deterioration (an increase in the score from baseline of ≥ 10 points) that is confirmed at the subsequent assessment (at least 14 days apart) or death (by any cause) in the absence of a clinically meaningful symptom deterioration, regardless of whether the patient withdraws from study drug or receives another anticancer therapy prior to symptom deterioration. Death will be included as an event only if the death occurs within 2 visits of the last PRO assessment where the symptom change could be evaluated.

Patients with a single deterioration and no further assessments will be treated as deteriorated in the analysis. Patients whose symptoms (as measured by EORTC QLQ-C30) have not shown a clinically meaningful deterioration and who are alive at the time of the analysis will be censored at the time of their last PRO assessment where the symptom could be evaluated. Also, if symptoms deteriorate after 2 or more missed PRO assessment visits or the patient dies after 2 or more missed PRO

assessment visits, the patient will be censored at the time of the last PRO assessment where the symptom could be evaluated. If a patient has no evaluable visits or does not have baseline data, he/she will be censored at Day 1.

The analysis of time to symptom deterioration will be done with a subset of patients who have baseline scores of ≤ 90 .

Time to quality of life/function deterioration

For QoL, time to deterioration will be defined as the time from start of study drug until the date of the first clinically meaningful deterioration (a decrease in the function scales or the global health status/QoL from baseline of ≥ 10 points) that is confirmed at the subsequent assessment (at least 14 days apart) or death (by any cause) in the absence of a clinically meaningful deterioration, regardless of whether the patient withdraws from study drug or receives another anticancer therapy prior to QoL/function deterioration. Death will be included as an event only if the death occurs within 2 visits of the last PRO assessment where the QoL/function change could be evaluated.

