- Time to symptom deterioration: defined as the time from start of study drug until the date of the first clinically meaningful symptom deterioration (a decrease in the score from baseline of  $\geq 10$  points) that is confirmed at the subsequent assessment (at least 14 days apart) or death (by any cause) in the absence of a clinically meaningful symptom deterioration, regardless of whether the patient withdraws from study drug or receives another anticancer therapy prior to symptom deterioration. Death will be included as an event only if the death occurs within 2 visits of the last PRO assessment where the symptom change could be evaluated.  
Patients whose QoL (as measured by EORTC QLQ-C30) have not shown a clinically meaningful deterioration and who are alive at the time of the analysis will be censored at the time of their last PRO assessment where the QoL/function could be evaluated. Also, if QoL deteriorates after 2 or more missed PRO assessment visits or the patient dies after 2 or more missed PRO assessment visits, the patient will be censored at the time of the last PRO assessment where QoL/function could be evaluated. If a patient has no evaluable visits or does not have baseline data, he/she will be censored at Day 1.
- Time to quality of life/ function deterioration: defined as the time from start of study drug until the date of the first clinically meaningful deterioration (a decrease in the function scales or the global health status/QoL from baseline of  $\geq 10$  points) that is confirmed at the subsequent assessment (at least 14 days apart) or death (by any cause) in the absence of a clinically meaningful deterioration, regardless of whether the patient withdraws from study drug or receives another anticancer therapy prior to QoL/function deterioration. Death will be included as an event only if the death occurs within 2 visits of the last PRO assessment where the QoL/function change could be evaluated.
- Symptom improvement rate: defined as the number (%) of patients with 2 consecutive assessments at least 14 days apart that show a clinically meaningful improvement (an increase from baseline score  $\geq 10$  points for EORTC QLQ-C30 symptom scales/items) in that symptom from baseline.

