#### Endpoints analyzed:

- Change from baseline in European Organisation for Research and Treatment of Cancer Quality of Life Questionnaire Core 30 items (EORTC QLQ-C30) and Questionnaire-Lung Cancer 13 (EORTC QLQLC13):

Scores for the QLQ-C30 and QLQ-LC13 questionnaires will be calculated according to published scoring manuals or the developer's guidelines. Raw scores from scales in both questionnaires will be standardized by linear transformation so that they range from 0 to 100. Higher scores for symptom items indicate greater symptom severity, while higher scores for function and global health status/QoL items indicate better function and health status/QoL. For both questionnaires, a clinically meaningful change will be prespecified as an absolute change in score from baseline of  $\geq 10$  points (either deterioration or improvement). For the five key disease-related symptoms (cough, dyspnea, and chest pain [QLQ-LC13], and fatigue and appetite loss [QLQ-C30]), changes at each visit from baseline to disease progression or end of follow-up (whichever came first) will be analyzed using a mixed model for repeated measures (MMRM) to derive an overall adjusted mean change from baseline, reflecting the average treatment effect over visits. The model assumes PROs will be collected at multiple visits per

patient. Visits with >75% missing data will be excluded from the analysis. The MMRM included treatment, age at baseline (<65 vs ≥65 years), sex, smoking history (smoker vs non-smoker) and visit interaction as fixed factors, and baseline score as a covariate; the model further adjusted for baseline score-by-visit interaction.

Summaries of original and change from baseline values of each symptom scale/item, the global HRQoL score, and each functional domain will be reported by visit.

Time to symptom deterioration and time to quality of life / function deterioration (defined in 4.2.2) will be analyzed by product limit methods to provide summaries of the number and percentage of patients experiencing a clinically meaningful deterioration or death, the median time to deterioration together with the corresponding 95% CIs, as well as the Kaplan-Meier plot. An stratified log-rank test adjusted for therapy will be used with HR s and 95% CIs calculated using a stratified Cox proportional hazards model.

Symptom improvement rate and Quality of life / function improvement (defined in 4.2.2) will be summarized.

- Changes from baseline in PRO-CTCAE:

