## **6.2 Handling of missing data**

Missing values will not be considered for calculating percentages or any other descriptives, meaning that only valid values will be presented. The number of missing data will be provided for every analysed variable. No use of any method or imputation of data for the handling of missing data is foreseen.

For the questionnaires EORTC QLQ-C30, EORTC QLQ-LC13 and PRO-CTCAE, for each subscale, if < 50% of the subscale items are missing, then the subscale score will be divided by the number of non missing items and multiplied by the total number of items on the subscales. If at least 50% of the items are missing, then that subscale will be treated as missing. Missing single items are treated as missing. The reason for any missing questionnaire will be identified and recorded. If there is evidence that the missing data are systematic, missing values will be handled to ensure that any possible bias is minimized.

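### The SAP omits two protocol rules for time to symptom deterioration, so a worsening at a patient's last questionnaire has no assigned outcome and the reported times will tend to be too long

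*SAP*

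**What the plan says.** Protocol 9.5.2.3 defines time to symptom deterioration on the QLQ-C30 as time to a first increase of at least 10 points that is confirmed at the next assessment, or death. It then adds two rules:

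- "Patients with a single deterioration and no further assessments will be treated as deteriorated in the analysis".
- "The analysis of time to symptom deterioration will be done with a subset of patients who have baseline scores of" 90 or less.

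It also says that QLQ-LC13 symptoms will be summarised in the way set out for the C30.

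SAP 4.2.2.2 keeps the confirmation requirement ("that is confirmed at the subsequent assessment (at least 14 days apart) or death (by any cause")) and a limit on deaths: "Death will be included as an event only if the death occurs within 2 visits of the last PRO assessment" at which the symptom could be evaluated. It also keeps the two-missed-visits rule and Day 1 censoring. Its censoring sentence covers "Patients whose QoL (as measured by EORTC QLQ-C30) have not shown a clinically meaningful deterioration and who are alive at the time of the analysis", who are censored at their last evaluable questionnaire. Neither added protocol rule appears.

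Nothing elsewhere in the SAP restores them. Section 5.2.2 refers back: "Time to symptom deterioration and time to quality of life / function deterioration (defined in 4.2.2) will be analyzed by product limit methods". Section 6.2 states: "No use of any method or imputation of data for the handling of missing data is foreseen". No reason for the difference is given.

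**The concern.** A confirmation requirement needs a rule for worsenings that cannot be confirmed. In extensive-stage small-cell lung cancer, patients who feel worse are plausibly more likely to stop completing questionnaires. If they are censored at the visit where they worsened, the censoring is informative, and Kaplan-Meier treats them as having the same outlook as patients who remain under observation. The curve is then too high and the median too long. The same question arises for continuing patients at any data cut, such as the February 2022 quality-of-life analysis in SAP section 7, if their most recent score is a first worsening.

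Protocol 9.5.2.3 pre-specifies time to deterioration for seven key symptoms: cough, hemoptysis, dyspnea, chest pain, insomnia, fatigue and appetite loss. SAP 5.2.2 will report medians, confidence intervals and plots for time to symptom deterioration.

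**Working it through.** The documents give no event count, rate or median for this endpoint, so there is no stated figure to reproduce. The check is a comparison of the texts, followed by an illustration on assumed rates.

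**1. One patient under each document.** The patient worsens by at least 10 points at week 9 and completes no later questionnaire.

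- Protocol: event at week 9.
- SAP, patient alive: no confirmed event. The natural default is censoring at week 9, though the SAP does not say so.
- SAP, death within two visits: event, dated at death rather than at week 9.

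The SAP therefore gives fewer events, or later ones, and never earlier ones.

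**2. Simple scaling.** With exponential event times, recoding a random fraction p of events as censored multiplies the hazard by (1 − p), so the median is multiplied by 1/(1 − p). For assumed p of 20%, 30% and 40% the factor is 1/0.8 = 1.25, 1/0.7 = 1.43 and 1/0.6 = 1.67. This ignores the death rule.

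**3. Simulation with the death rule.** There were 20,000 patients per scenario, with visits at weeks 3, 6, 9 and 12 and then every 4 weeks. Every rate is an assumption:

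- worsening at 8% or 15% per visit;
- 60% of worsenings confirmed if reassessed;
- unrelated drop-out of 3% per visit;
- 10%, 30% or 50% of worsenings followed by no further questionnaire;
- 0%, 30% or 60% of those patients dying within two visits.

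Medians are in weeks, with the direction of worsening taken as in the protocol.

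| Worsening per visit | Stop after worsening | Protocol rule | SAP, 0% early deaths | SAP, 30% | SAP, 60% |
|---|---|---|---|---|---|
| 8% | 10% | 52 | 64 | 60 | 56 |
| 8% | 30% | 44–48 | 80 | 64 | 56 |
| 8% | 50% | 40 | not reached | 76 | 56 |
| 15% | 10% | 28 | 32 | 32 | 28 |
| 15% | 30% | 24 | 44 | 36 | 28 |
| 15% | 50% | 20 | 64 | 40 | 28 |

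In all 18 scenarios the SAP median was equal or longer. The share event-free at 24 weeks was higher under the SAP in every one, by about 2 points (70% against 72%) to 32 points (42% against 74%). These are differences between two rules, not bias against a known truth: some lone worsenings counted by the protocol would not have been confirmed.

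**4. Baseline rule.** SAP 4.2.2.2 scores symptoms as (RS − 1)/range × 100. A single four-point item has range 4 − 1 = 3 and can score only 0, 33.3, 66.7 or 100. A baseline above 90 therefore means 100, and no further worsening is possible. If a fraction f of patients start there, and deaths and drop-out are ignored, the event-free curve is f + (1 − f)S(t). That is f(1 − S(t)) too high, or f/2 where S(t) = 0.5. The documents give no value for f.

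**The case against.** Several points on the other side have force.

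- **The SAP does not expressly censor these patients.** A reader might infer that it does. Its censoring sentence covers patients who have not shown a meaningful deterioration, and SAP 5.2.2 defines a meaningful change as 10 points without mentioning confirmation. A lone worsening is therefore unassigned. This stands, but an unassigned case in an event definition still needs a rule.
- **Early deaths still count.** This also stands, and it matters: with 15% worsening and 30% stopping, the SAP median falls from 44 to 28 weeks as early deaths rise from 0% to 60%.
- **Questionnaires may continue after treatment.** Protocol 8.2.7 describes completion "using a paper format questionnaire on day 1 of every cycle", and a reader might infer that nothing is collected once treatment stops, so that the endpoint is really an on-treatment one. The documents do not support that. The questionnaire rows of the schedule are not visible in the public copy, and protocol 7.1.1 has data collection continue after treatment stops. Both documents also define the endpoint irrespective of withdrawal from study drug. The gap affects anyone whose questionnaires end, whenever that happens.
- **The function and quality-of-life scales.** A reader might infer that they lost the same rule. They did not: the protocol states it for symptoms only.
- **Low stakes.** The study is single-arm and descriptive, with no formal hypothesis. The protocol's objectives table lists change from baseline rather than time to deterioration, and protocol 9.5.2.3 leaves analysis detail to the SAP. This limits the weight of the point. But leaving detail to the SAP does not explain silently dropping a stated rule.

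**Conclusion.** The concern holds for the symptom endpoints. Two protocol rules are missing from the SAP without explanation. The symptom censoring text in the SAP closely follows the protocol's function and quality-of-life text, which suggests a drafting slip rather than a decision, though that is an inference.

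The effect is to lengthen time to symptom deterioration relative to the protocol's rule. The direction follows from the definitions, provided that an unassigned worsening is censored by default. The size cannot be derived from the documents: it depends on how often a first worsening falls on the last questionnaire and how many of those patients die within two visits. The tabulated figures show sensitivity to assumed rates and are not estimates for this trial. The baseline omission acts in the same direction and, for single items, concerns only patients already at the maximum score.

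One condition applies. SAP 4.2.2.2 defines symptom deterioration as a decrease of at least 10 points, although it also says that higher symptom scores are worse. Read literally, the event would be an improvement. The argument here assumes that this separate error is corrected to the protocol's increase.

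**What to change.** In SAP 4.2.2.2, for the QLQ-C30 symptom scales and items and by cross-reference the QLQ-LC13 symptoms:

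1. State that a single deterioration with no further assessment is an event at that assessment.
2. Restrict the time-to-symptom-deterioration analysis to patients with baseline scores of 90 or less.
3. In the same definition, change the direction to an increase of at least 10 points. Take the sign from the protocol's time-to-symptom-deterioration definition, not from its visit-response table, which codes a symptom increase as improvement.

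If leaving out the two rules was intended, give the reason and report the analysis under both rules as a sensitivity analysis. If the team also wants the lone-worsening rule for function and quality-of-life scales, present it as a new choice and not as restoring the protocol. Keep the wording that the endpoint applies irrespective of withdrawal from study drug.

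The cost is a few sentences of SAP text and the matching programming. No new data or visits are needed.

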PFS (days) = Date of event or Censor date – treatment start date +1

Patients who have not progressed or died at the time of analysis will be censored at the time of the latest date of assessment from their last evaluable assessment. However, if the patient progresses or dies after 2 or more missed visits, the patient will be censored at the time of the latest evaluable assessment prior to the 2 missed visits. If the patient has no evaluable visits or does not have baseline data, he/she will be censored at Day 1 unless he/she dies within 2 visits of baseline, in which case the date of death is the event date.

OS: Defined as the time from the first date of treatment until death due to any cause.

OS (days) = Death date or Censor date - treatment start date +1

Any patient not known to have died at the time of analysis will be censored based on the last recorded date on which the patient was known to be alive.

ORR: Based on Investigator–assessed response to treatment of CR and PR, per RECIST1.1.

DoR: Defined as the time from the date of first documented response per RECIST1.1 until the first date of documented progression per RECIST1.1 or death in the absence of disease progression.

DoR (days) = Date of PFS event or censoring – Date of first response +1

The end of response should coincide with the date of progression or death from any cause used for the PFS endpoint. If a patient does not progress following a response, then the patients' DoR will be censored at the PFS censoring time. DoR will not be defined for those patients who do not have a documented response.

Time to symptom deterioration (EORTC QLC-C30 and QLC-LC13): Defined as the time from start of study drug until the date of the first clinically meaningful symptom deterioration that is confirmed at the subsequent assessment or death (by any cause) in the absence of a clinically meaningful symptom deterioration, regardless of whether the patient withdraws from study drug or receives another anticancer therapy prior to symptom deterioration.

Change from baseline (EORTC QLC-C30 and QLC-LC13, PRO-CTCAE): Defined as the post-treatment value minus the value at baseline. The % change from baseline will be calculated as (postbaseline value - baseline value) / baseline value x 100.

Treatment duration: Defined as Treatment end date - Treatment start date +1; will be summarized.

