#### Endpoints analyzed:

- Progression-free survival (PFS): This analysis will be performed for the Intention-to-Treat population (ITT). PFS is defined as the time from the first date of treatment until the date of objective disease progression or death (by any cause in the absence of progression) regardless of whether the patient withdraws from IP or receives another anticancer therapy prior to progression.

**PFS (days)** = Date of event or Censor date – treatment start date +1

Patients who have not progressed or died at the time of analysis will be censored at the time of the latest date of assessment from their last evaluable assessment. However, if the patient progresses or dies after 2 or more missed visits, the patient will be censored at the time of the latest evaluable assessment prior to the 2 missed visits. If the patient has no evaluable visits or does not have baseline data, he/she will be censored at Day 1 unless he/she dies within 2 visits of baseline, in which case the date of death is the event date.

The PFS analysis will be based on the programmatically derived RECIST 1.1 using the Investigator tumor assessments. It will be analysed PFS, PFS at 6 months (6mPFS) and PFS at 12 months (12mPFS).

- Objective response rate (ORR): This outcome will be analysed for the responder's analysis set. The ORR will be based on the programmatically derived RECIST 1.1 using the investigator tumor data.
- Duration of response (DoR): This outcome will be analysed for the responder's analysis set. DoR is defined as the time from the date of first documented response per RECIST1.1 until the first date of documented progression per RECIST1.1 or death in the absence of disease progression.

DoR (days) = Date of PFS event or censoring – Date of first response +1

The end of response should coincide with the date of progression or death from any cause used for the PFS endpoint. If a patient does not progress following a response, then the patients' DoR will be censored at the PFS censoring time. DoR will not be defined for those patients who do not have a documented response. It will be analysed DoR and DoR at 1 year (DoR12)

- Overall survival (OS): This analysis will be performed for the Intention-to-Treat population (ITT). OS is defined as the time from the first date of treatment until death due to any cause.

OS (days) = Death date or Censor date - treatment start date +1

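### After two or more missed PRO visits, the time-to-deterioration rule censors at the last evaluable questionnaire, not the last one before the gap, so patients seen to deteriorate stay at risk as event-free

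*SAP*

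**What the plan says.** SAP 4.2.2.2 sets the trigger as: "if QoL deteriorates after 2 or more missed PRO assessment visits or the patient dies after 2 or more missed PRO assessment visits". In that case "the patient will be censored at the time of the last PRO assessment where QoL/function could be evaluated". The sentence stands under time to symptom deterioration, although it is worded for QoL/function. The SAP's own item on time to QoL/function deterioration has no censoring text.

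Protocol 9.5.2.3 has the rule twice. For symptoms, "the patient will be censored at the time of the last PRO assessment where the symptom could be evaluated"; for QoL/function the wording matches the SAP. QLQ-LC13 is to be summarised in the same way as QLQ-C30, so it inherits the rule.

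The PFS rule in Protocol 9.4 and SAP 4.2.2.1 meets the same situation with a different date. The SAP version reads: "the patient will be censored at the time of the latest evaluable assessment prior to the 2 missed visits".

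Questionnaires are completed "on day 1 of every cycle" (Protocol 8.2.7). SAP 5.2.2 refers back to the definitions in section 4.2.2 and reports "the median time to deterioration together with the corresponding 95% CIs, as well as the Kaplan-Meier plot".

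**The concern.** A missed-visit rule exists because, when a patient returns already worse, nobody knows when in the gap the worsening happened. The usual answer is to stop the patient's follow-up at the last visit before the gap. The PRO rule names a different visit. The questionnaire that shows the worsening is itself evaluable, and so are any later ones. The last evaluable assessment therefore cannot precede the deterioration.

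A patient known to have deteriorated is thus counted as deterioration-free up to that visit or beyond it. Protocol 9.5.2.3 pre-specifies time to deterioration for several key symptoms, and a single-arm study has no comparator in which the same bias could cancel. SAP section 7 schedules a QoL analysis for February 2022, so the rule would be programmed early.

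**Working it through.** The documents report no figure that depends on this rule, so there is none to reproduce. The check has three steps.

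**1. One patient on the protocol's grid.** With four chemotherapy cycles, PRO days are 1, 22, 43, 64 and 85, then every 28 days (113, 141, and so on). Suppose questionnaires on Days 1 and 22, none on Days 43 and 64, a worsening of at least 10 points on Day 85 confirmed on Day 113, and a last questionnaire on Day 141.

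- Rule as written: censored at Day 141, or at Day 85 at the earliest if no later questionnaire exists.
- PFS-style rule: censored at Day 22.
- Extra event-free time: 141 − 22 = 119 days; at the least, 85 − 22 = 63 days.

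**2. Direction of the bias, without assumptions.** Both rules censor these patients, so the counted events and their dates are identical. Only the risk sets differ, and under the rule as written each is at least as large. The Kaplan-Meier estimate is S(t) = ∏(1 − d/n) over event times up to t. With d unchanged and n equal or larger, every factor is equal or larger. S(t) under the rule as written can therefore never be lower, and the median can never be shorter.

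**3. Size, under assumptions.** The documents give no missing-visit rate, so all rates below are assumed.

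*(a) Missed visits at random.* 20,000 patients per setting; exponential time to deterioration; visits at weeks 0, 3, 6, 9 and 12, then every 4 weeks; each visit missed independently. The comparison is the rule as written minus pre-gap censoring, at 9 months.

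| True median; PRO follow-up | 10% missed | 20% missed | 30% missed |
|---|---|---|---|
| 4 months; 1.5 months plus a median of 6 | about 1 point | about 4 points (30% v 26%) | about 8 points (37% v 29%) |
| 4 months; 1 month plus a median of 2 after deterioration, capped at 18 months | about 0.6 | about 2 | about 4.5 |

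With a true median of 8 months and the longer follow-up, the excess is about 0.5 to 4 points. In the first row, about 2%, 8% and 17% of observed deteriorations are affected. Extra event-free time per affected patient averages about 8 to 9 months with the longer follow-up and about 4 with the shorter. If follow-up has no cut-off at all, it can reach about 11 months.

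*(b) One two-visit gap in a fixed share of patients.* 8,000 patients per setting, questionnaires otherwise complete to Day 365; deterioration-free proportion at 12 months.

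| True median (days) | Share with a gap | Affected of 85 | Event at detection | Pre-gap | As written | Excess over pre-gap | Median, pre-gap → as written (days) |
|---|---|---|---|---|---|---|---|
| 90 | 10% | 2.5 | 0.059 | 0.062 | 0.089 | 0.027 | 113 → 113 |
| 90 | 20% | 4.9 | 0.057 | 0.063 | 0.115 | 0.052 | 113 → 113 |
| 90 | 40% | 10.1 | 0.062 | 0.075 | 0.181 | 0.106 | 113 → 141 |
| 180 | 10% | 1.5 | 0.245 | 0.251 | 0.263 | 0.012 | 197 → 197 |
| 180 | 20% | 3.6 | 0.244 | 0.257 | 0.286 | 0.029 | 197 → 225 |
| 180 | 40% | 6.5 | 0.248 | 0.273 | 0.325 | 0.052 | 225 → 253 |

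The excess is positive in every row, as step 2 requires. The median is unchanged in three rows and one visit interval (28 days) longer in three.

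**The case against.** The strongest reply is that the text is loosely worded, not wrong. One clause covers both deterioration and death after a gap, and for a death the last evaluable questionnaire can only be the one before the gap. The same paragraph also uses the phrase relative to an event, when it counts a death only if it falls close to the last PRO assessment. The pre-gap date was very probably meant. That speaks to intent but does not clear the text. The sentence just before uses the same phrase for patients who never deteriorated, and there it means the end of PRO follow-up. Where the authors wanted the limit they wrote it, as in the PFS rule: "censored at the time of the latest evaluable assessment prior to the 2 missed visits". A programmer following the PRO text would censor too late.

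Three other points stand and limit the finding:

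- **Outcome-dependent censoring is not itself the defect.** Pre-gap censoring also acts on patients because they deteriorated. In the second row of table (b), moving from event at detection to pre-gap adds 0.063 − 0.057 = 0.006; the rule as written adds a further 0.115 − 0.063 = 0.052. Only the second amount belongs here.
- **The size depends on follow-up.** Shorter PRO follow-up after deterioration roughly halves the excess.
- **The stakes are modest.** The endpoint is secondary and descriptive, in about 85 patients. The protocol's own 95% precision for a proportion at that size is about ±9 to ±11 points, so a shift of 1 to 4 points lies within sampling error. It is still a one-directional bias, which the confidence interval does not describe.

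**Conclusion.** The point holds. As written, the rule keeps patients who deteriorate after two or more missed PRO visits at risk and event-free up to or beyond the observed deterioration, so deterioration-free proportions are biased upwards. The direction follows from the text alone; the size does not. With 10% to 30% of visits missed independently, about 2% to 17% of observed deteriorations are affected. The 9-month proportion is overstated by about 0.5 to 8 points, with about 4 to 9 extra event-free months per affected patient. The larger excess in table (b), 0.106, is at 12 months with 40% of patients having a gap and otherwise complete follow-up, and is not a headline figure.

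A reader might infer more than the documents support:

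- That the median is biased upwards on every scale. It cannot fall, but in simulation it moved by zero to two visit intervals and was often unchanged.
- That deaths after a gap are also mishandled. They are not, because no questionnaire follows them.
- That the number of events changes. Both rules censor these patients.
- That the effect is known to be large. No missing-visit rate is given, and at 10% missed the overstatement is about 1 point or less.

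**What to change.** Change the censoring date in three places: the SAP 4.2.2.2 rule and the two rules in Protocol 9.5.2.3 (symptoms, and QoL/function). It should be the last evaluable PRO assessment before the run of two or more consecutive missed visits that immediately precedes the deterioration or death. In the SAP, state that the rule applies to both the symptom and the QoL/function endpoints, since the text now sits under symptoms only. The sentence for patients who never deteriorate can stay as it is.

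This matches the plan's PFS convention. It costs one clause per place and needs no new data or assessments. Reported deterioration-free proportions become slightly lower. It is best settled before the QoL analysis is programmed.
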